## **10.4 APPENDIX 4: CONTRACEPTIVE GUIDANCE AND COLLECTION OF PREGNANCY INFORMATION**

### **DEFINITIONS:**

#### **Woman of childbearing potential (WOCBP)**

A woman is considered fertile following menarche and until becoming post-menopausal unless permanently sterile (see below).

#### **Women in the following categories are not considered WOCBP**

1. Premenarchal.
2. Female with 1 of the following:
  - Documented hysterectomy,
  - Documented bilateral salpingectomy,
  - Documented bilateral oophorectomy.

Note: Documentation can come from the site personnel's: review of the participant's medical records, medical examination, or medical history interview.

3. Postmenopausal female.
  - A postmenopausal state is defined as no menses for at least 12 months without an alternative medical cause. A high follicle stimulating hormone (FSH) level in the postmenopausal range may be used to confirm a postmenopausal state in women not using hormonal contraception or hormonal replacement therapy (HRT). However, in the absence of 12 months of amenorrhea, a single FSH measurement is insufficient,
  - Females on HRT and whose menopausal status is in doubt will be required to use one of the non-estrogen hormonal highly effective contraception methods if they wish to continue their HRT during the study. Otherwise, they must discontinue HRT to allow confirmation of postmenopausal status before study enrollment.

### **CONTRACEPTION GUIDANCE**

#### **Female participants**

Female participants of childbearing potential are eligible to participate if they agree to use a highly effective method of contraception consistently and correctly as described in [Table 9](#).

In addition, WOCBP must refrain from donating ova for the duration of the study and for 5 weeks after the last dose of study intervention.

**Table 9 - Contraceptives allowed during the study**

---

**CONTRACEPTIVESa ALLOWED DURING THE STUDY INCLUDE:**

---

**Highly effective methodsb that are user dependent** *Failure rate of <1% per year when used consistently and correctly.*

---

Combined (estrogen and progestogen containing) hormonal contraception associated with inhibition of ovulationc

- Oral
  - Intravaginal
  - Transdermal
  - Injectable
- 

Progestogen only hormonal contraception associated with inhibition of ovulationc

- Oral
  
  - Injectable
- 

**Sexual abstinence**

Sexual abstinence is considered a highly effective method only if defined as refraining from heterosexual intercourse during the entire period of risk associated with the study intervention. The reliability of sexual abstinence needs to be evaluated in relation to the duration of the study and the preferred and usual lifestyle of the participant.

---

**Highly effective methodsb that have low user dependency** *Failure rate of <1% per year when used consistently and correctly.*

---

- Implantable progestogen-only hormone contraception associated with inhibition of ovulationb
  - Intrauterine device (IUD)
  
  - Intrauterine hormone-releasing system (IUS)b
  
  - Bilateral tubal occlusion
  - Vasectomized partner
- (Vasectomized partner is a highly effective contraception method provided that the partner is the sole sexual partner of the WOCBP and the absence of sperm has been confirmed. If not, an additional highly effective method of contraception should be used. Spermatogenesis cycle is approximately 90 days.)*
- 

**Acceptable methodsd**

---

- Progestogen-only oral hormonal contraception where inhibition of ovulation is not the primary mode of action
  - Male or female condom with or without spermicidee
  - Cervical cap, diaphragm, or sponge with spermicide
  - A combination of male condom with either cervical cap, diaphragm, or sponge with spermicide (double-barrier methods)c
- 

NOTES:

- a Contraceptive use by men or women should be consistent with local regulations regarding the use of contraceptive methods for those participating in clinical studies.
- b Failure rate of <1% per year when used consistently and correctly. Typical use failure rates may differ from those when used consistently and correctly.
- c Male condoms must be used in addition to hormonal contraception. If locally required, in accordance with Clinical Trial Facilitation Group (CTFG) guidelines, acceptable contraceptive methods are limited to those which inhibit ovulation as the primary mode of action.
- d Considered effective, but not highly effective - failure rate of ≥1% per year. Periodic abstinence (calendar, symptothermal, post-ovulation methods), withdrawal (coitus interruptus), spermicides only, and lactational amenorrhoea method (LAM) are not acceptable methods of contraception.
- e Male condom and female condom should not be used together (due to risk of failure with friction).
-

### **PREGNANCY TESTING:**

- WOCBP should only be included after a confirmed menstrual period and a negative highly sensitive serum pregnancy test.
- Additional pregnancy testing during the intervention period as presented in the SoA (see [Section 1.3](#)) and as required locally.
- Pregnancy testing will be performed whenever a menstrual cycle is missed or when pregnancy is otherwise suspected.

### **COLLECTION OF PREGNANCY INFORMATION:**

#### **Male participants with partners who become pregnant**

[figure not shown]
- The Investigator will attempt to collect pregnancy information on any male participant's female partner who becomes pregnant while the male participant is in this study. This applies only to male participants who receive study intervention.
- After obtaining the necessary signed informed consent from the pregnant female partner directly, the Investigator will record pregnancy information on the appropriate form and submit it to the Sponsor within 24 hours of learning of the partner's pregnancy. The female partner will also be followed to determine the outcome of the pregnancy. Information on the status of the mother and child will be forwarded to the Sponsor. Generally, the follow-up will be no longer than 6 to 8 weeks following the estimated delivery date. Any termination of the pregnancy will be reported regardless of fetal status (presence or absence of anomalies) or indication for the procedure.

#### **Female participants who become pregnant**

- The Investigator will collect pregnancy information on any female participant who becomes pregnant while participating in this study. Information will be recorded on the appropriate form and submitted to the Sponsor within 24 hours of learning of a participant's pregnancy. The participant will be followed to determine the outcome of the pregnancy. The Investigator will collect follow-up information on the participant and the neonate and the information will be forwarded to the Sponsor. Generally, follow-up will not be required for longer than 6 to 8 weeks beyond the estimated delivery date. Any termination of pregnancy will be reported, regardless of fetal status (presence or absence of anomalies) or indication for the procedure.
- Any pregnancy complication or elective termination of a pregnancy will be reported as an AE or SAE. A spontaneous abortion is always considered to be an SAE and will be reported as such. Any post-study pregnancy related SAE considered reasonably related to the study intervention by the Investigator will be reported to the Sponsor as described in [Section 8.3.4](#). While the Investigator is not obligated to actively seek this information in former study participants, he or she may learn of an SAE through spontaneous reporting.
- Any female participant who becomes pregnant while participating in the study will discontinue study intervention or be withdrawn from the study.

## 10.5 APPENDIX 5: LIVER SAFETY: SUGGESTED ACTIONS AND FOLLOW-UP ASSESSMENTS

### INCREASE IN ALT

**In ANY CASE, FOLLOW** the instructions listed in the box below:

1. **INFORM** the Site Monitor who will forward the information to the Study Manager
2. **INVESTIGATE** specifically for malaise with or without loss of consciousness, dizziness, and/or hypotension and/or episode of arrhythmia in the previous 72 hours; rule out muscular injury
3. **PERFORM** the following tests:
  - LFTs: AST, ALT, alkaline phosphatase, total and conjugated bilirubin and prothrombin time / INR
  - CPK, serum creatinine, complete blood count
  - Anti-HAV IgM, anti-HBc IgM (HBV-DNA if clinically indicated), anti-HCV and HCV RNA, anti-CMV IgM and anti-HEV IgM antibodies
  - Depending on the clinical context, check for recent infection with EBV, herpes viruses, and toxoplasma
  - Hepatobiliary ultrasonography (or other imaging investigations if needed)
4. **CONSIDER** Auto-antibodies: antinuclear, anti-DNA, anti-smooth muscle, anti-LKM
5. **CONSIDER** consulting with hepatologist
6. **CONSIDER** patient hospitalisation if INR>2 (or PT<50%) and/or central nervous system disturbances suggesting hepatic encephalopathy
7. **MONITOR LFTs after discontinuation of IMP:**
  - As closely as possible (or every 48 hours) until stabilization, then every 2 weeks until return to normal/baseline or clinical resolution.
8. **FREEZE** serum sample (5ml x 2)
9. **In case of SUSPICION of GILBERT Syndrome**, a DNA diagnostic test should be done

\*If unable to retest in 72 hours, use original lab results to decide on further reporting/monitoring/discontinuation.

Note:

- “Baseline” refers to ALT sampled at baseline visit; or if baseline value unavailable, to the latest ALT sampled before the baseline visit. The algorithm does not apply to the instances of increase in ALT during screening.
- See [Section 10.3](#) for guidance on safety reporting.
- Normalization is defined as ≤ULN or baseline value, if baseline value is >ULN.

## **10.6 APPENDIX 6: MEDICAL DEVICE INCIDENTS: DEFINITION AND PROCEDURES FOR RECORDING, EVALUATING, FOLLOW-UP, AND REPORTING**

Not applicable.

## **10.7 APPENDIX 7: COUNTRY-SPECIFIC REQUIREMENTS**

Not applicable.

## **10.8 APPENDIX 8: ABBREVIATIONS**

AE:	adverse event
AESI:	adverse event of special interest, adverse event of special interest
AIA:	anti-insulin aspart antibody
ALT:	alanine aminotransferase
ARAC:	Allergic Reaction Adjudication Committee
AST:	aspartate aminotransferase
AUC:	area under the concentration curve
BID:	twice daily
BMI:	body-mass index, body-mass index
BP:	blood pressure
CFR:	Code of Federal Regulations
CGM:	continuous glucose monitoring
CI:	confidence interval
CIOMS:	Council for International Organizations of Medical Sciences
Cmax:	maximum concentration
CONSORT:	Consolidated Standards of Reporting Trials
DNA:	deoxyribonucleic acid
ECG:	electrocardiogram
eCRF:	electronic case report form
EOT:	end of treatment, end of treatment
EU:	European Union
FDA:	Food and Drug Administration
FPG:	fasting plasma glucose, fasting plasma glucose
FSH:	follicle-stimulating hormone, follicle-stimulating hormone
GCP:	Good Clinical Practice
GDPR:	Global Data Protection Regulation
GFR:	glomerular filtration rate
H0:	null hypothesis
H1:	alternative hypothesis 1
HbA1c:	glycated hemoglobin A1c
hCG:	human chorionic gonadotropin
HIPAA:	Health Insurance Portability and Accountability Act
HR:	heart rate

HRT:	hormonal replacement therapy
IB:	investigator's brochure
ICF:	informed consent form
ICH:	International Conference on Harmonization
IEC:	Independent Ethics Committee
IFCC:	International Federation of Clinical Chemistry
INR:	international normalized ratio
IRB:	Institutional Review Board
IRT:	interactive response technology, interactive response technology
ITT:	intent to treat
IUD:	intrauterine device
IUS:	intrauterine hormone-releasing device
MDI:	multiple dose injection
MDRD:	modification of diet in renal disease
MedDRA:	Medical Dictionary for Regulatory Activities
NGSP:	National Glycohemoglobin Standardization Program
NIMP:	noninvestigational medicinal product
PD:	pharmacodynamic(s)
PHS:	Public Health Service
PK:	Pharmacokinetic(s)
PP:	per protocol
PPG:	postprandial plasma glucose
QD:	once daily
RBC:	red blood cells
SAE:	serious adverse event, serious adverse event
SAP:	statistical analysis plan
SC:	subcutaneous
SMPG:	self-measured plasma glucose, self-measured plasma glucose
SoA:	schedule of activities
SUSAR:	suspected unexpected serious adverse reaction
T1DM:	type 1 diabetes mellitus
TEAE:	treatment-emergent adverse event
Tmax:	time of maximum concentration
ULN:	upper limit of the normal
US:	United States
WBC:	white blood cells
WOCBP:	woman of childbearing potential, woman of childbearing potential

## 10.9 APPENDIX 9: PROTOCOL AMENDMENT HISTORY

The Protocol Amendment Summary of Changes Table for the current amendment is located directly before the Table of Contents (TOC).

### Amendment 01 (27 February 2019)

This amended protocol (amendment 01) is considered to be substantial based on the criteria set forth in Article 10(a) of Directive 2001/20/EC of the European Parliament and the Council of the European Union.

## OVERALL RATIONALE FOR THE AMENDMENT

The standardized meal test has been removed from this study because the Food and Drug Administration (FDA) noted several safety and methodological concerns associated with its performance, and because the standardized meal test would not add clinical value to the study. The study can adequately evaluate the effect of switching on pharmacodynamics (PD) parameters without the standardized meal test through collection of data on insulin dose over time and on the most clinically relevant measures of glycemia (glycated hemoglobin A1c [HbA1c] and fasting plasma glucose [FPG]).

**Protocol amendment summary of changes table**

Section # and Name	Description of Change	Brief Rationale
Section 1.1 Synopsis; Section 1.2 Schema; Section 1.3 Schedule of Activities (SoA); Section 3 Objectives and Endpoints; Section 3.1 Appropriateness of Measurements; Section 4.1 Overall Design; Section 8.1.3 Standardized Meal Test; Section 8.1.4 Fasting Plasma Glucose; Appendix 2 Clinical Laboratory Tests	Standardized meal test has been removed	Several safety and methodological concerns were associated with standardized meal test performance and the standardized meal test would not have added any clinical value to the study
Section 1.1 Synopsis; Section 1.3 Schedule of Activities; Section 4.1 Overall Design; Section 6.5 Concomitant Therapy	Add recommendations regarding the management of participants' glycemia during the end of treatment (EOT) visit	Additional meal-time insulin will likely be needed in all patients for the duration of the 8-hour PK assessment. The listed insulins do not interfere with the reliability of PK measurements
Section 6.5 Concomitant Therapy	Mention that hypoglycemia will be managed as appropriate by administering carbohydrates according to the clinical judgement of the Investigator	Clarification
Section 4.3 Justification for Dose; Section 6.1 Study intervention(s) administered	Remove mention that the dosing regimen will be continued after each switch as it was used prior to the switch	To ensure consistency with the instruction that the Investigators should titrate SAR341402 and NovoLog according to the NovoLog label and their clinical judgement

Section # and Name	Description of Change	Brief Rationale
Appendix 4: Contraceptive guidance and collection of pregnancy information	All female participants with documented hysterectomy, bilateral salpingectomy, or bilateral oophorectomy are not considered of childbearing potential	Clarification
Section 5.2 Exclusion Criteria E21; Section 6.5 Concomitant Therapy	Exclusion of participants who used glucose lowering treatments other than the MDI and basal insulin regimen, as described in inclusion criterion I05 (including use of insulin pump therapy) during the screening period	To ensure a similar baseline in all participants in terms of insulin treatment before the start of the study treatment period
Section 5.1 Inclusion Criteria I01	Mention that participants must be at least 18 years old to participate to the study	Clarification
Section 5.1 Inclusion Criteria I06	Mention that participants must have "HbA1c less or equal to 10%" instead of "below 10% (inclusive)"	Clarification
Section 1.3 Schedule of Activities (SoA)	"Documentation of insulin dose" replaced with "Review of insulin dose"	Clarification that dose is documented on an ongoing basis but reviewed at the study visits
Section 1.3 Schedule of Activities (SoA)	Mention that blood samples for measuring fasting plasma glucose should be taken before IMP administration	Clarification
Section 6.1 Study intervention(s) administered	Mention that the Lantus dose may be increased by more than 10% if deemed necessary by the Investigator	Clarification
Section 8.3 Adverse Events and Serious Adverse Events	The following sentences were removed: "Note: Asymptomatic overdose has to be reported as a standard AE" "In case a participant experiences an event identified as a potential hypersensitivity reaction (an allergic reaction or an allergic-like reaction), this has to be reported as an AE and recorded in the eCRF on the AE page, selecting the "suspected allergic event" category; additional information is collected on specific eCRF forms. "	Asymptomatic overdose does not meet the definition of an AE  These operational details are subject to change
Appendix 3: Adverse events: definitions and procedures for recording, evaluating, follow-up, and reporting	Addition of guidance on which laboratory abnormalities to be considered clinically significant	To limit the number of queries related to laboratory abnormalities

## LIST OF ABBREVIATIONS AND DEFINITION OF TERMS

AEs:	adverse events
AESI:	adverse event of special interest
AIA:	anti-insulin aspart antibodies
ALP:	alkaline phosphatase
ALT:	alanine aminotransferases
ARAC:	Allergic Reaction Assessment Committee
ATC:	anatomical therapeutic chemical
BMI:	body mass index
CMQ:	customized MedDRA queries
COVID-19:	coronavirus disease 2019
CV:	coefficient of variance
DBP:	diastolic blood pressure
EOS:	end of study
EOT:	end of treatment
GFR:	glomerular filtration rate
HbA1c:	Glycated hemoglobin
HLGT:	high level group term
HLT:	high level term
IMP:	investigational medicinal product
IRT:	Interactive response technology
ITT:	intent-to-treat
KM:	Kaplan-Meier
LLOQ:	lower limit of quantification
LPLV:	last patient last visit
MDRD:	modification of diet in renal disease
MedDRA:	Medical Dictionary for Regulatory Activities
NAb:	neutralizing antibody
NIMP:	non-investigational medicinal product
PCSA:	Potentially clinically significant abnormality
PEOT:	premature end of trial
PT:	preferred term
RBC:	red blood cell
SAEs:	serious adverse events
SBP:	systolic blood pressure
SMQ:	standardized MedDRA query
SOC:	system organ class
T1DM:	type 1 diabetes mellitus
WHO-DD:	World Health Organization-Drug Dictionary

## 1 OVERVIEW AND INVESTIGATIONAL PLAN

This Statistical Analysis Plan (SAP) provides a comprehensive and detailed description of strategy and statistical technique to be used to realize the analysis of data for study SAR341402 /EFC15178.

### 1.1 STUDY DESIGN AND RANDOMIZATION

This is a randomized, open-label, active-controlled, 2-arm parallel-group multicenter Phase 3 trial comparing alternating use of SAR341402 solution for injection (100 U/mL) and NovoLog® (100 U/mL) versus continuous use of NovoLog in adults with type 1 diabetes mellitus (T1DM) also using insulin glargine (100 U/mL).

Participants with T1DM diagnosed for at least 12 months before screening, and who have been on a multiple daily injection regimen using NovoLog as mealtime insulin and insulin glargine 100 U/mL (Lantus®) as basal insulin for at least 12 weeks prior to screening, are eligible for the study. Patients who are not on NovoLog and insulin glargine (100 U/mL) for at least 12 weeks before screening are included in a run-in period of up to 12 weeks during which they are administered NovoLog and Lantus.

Patients are centrally randomized via Interactive Response Technology (IRT) (using permuted random block randomization schedule) in a 1:1 ratio to one of the following treatment groups:

- 4x4-week periods alternating use of SAR341402 and NovoLog (starting with NovoLog in the first treatment period and receiving SAR341402 during the last of the 4 treatment periods, “switching arm”) or
- 16 weeks continuous use of NovoLog (“non-switching arm”); see study design in [Section 1.4](#).

Insulin glargine 100 U/mL (Lantus) is to be administered as mandatory background therapy throughout the treatment period of the study and during the run-in period if applicable, and is considered as non-investigational medicinal product (NIMP). NovoLog is also considered as NIMP during the run-in period, if applicable.

Approximately 184 patients were planned to be randomized at approximately 33 sites in the US.

Randomization is being stratified by glycated hemoglobin (HbA1c) (<8.0%, ≥8.0%) measurement obtained at the screening visit (Visit 1).

## 1.2 OBJECTIVES

### 1.2.1 Primary objectives

The primary objective of this study is to demonstrate similarity in pharmacokinetics (PK) of SAR341402 and NovoLog after 4x4-week periods of alternating administration of SAR341402 and NovoLog compared to 16-week continuous use of NovoLog in participants with T1DM also using insulin glargine (100 U/mL).

### 1.2.2 Secondary objectives

The secondary objectives of this study are:

- To compare the effects of alternating administration of SAR341402 and NovoLog with continuous use of NovoLog on immunogenicity
- To evaluate the safety of alternating administration of SAR341402 and NovoLog versus continuous use of NovoLog
- To compare other PK parameters between the two treatment arms (alternating administration of SAR341402 and NovoLog and continuous use of NovoLog)

### 1.2.3 Tertiary/exploratory objectives

The tertiary/exploratory objectives of this study are:

- To compare the effects of alternating administration of SAR341402 and NovoLog with continuous use of NovoLog on insulin dose
- To compare the effects of alternating administration of SAR341402 and NovoLog with continuous use of NovoLog on glycemic control
- To compare clinical effects of treatment-emergent AIAs (anti-insulin aspart antibodies) on glycemic control, insulin dose and safety
- To compare the effects of alternating administration of SAR341402 and NovoLog with continuous use of NovoLog on additional immunogenicity parameters
- To compare clinical effects of treatment-emergent neutralizing antibodies on glycemic control and insulin dose

## 1.3 DETERMINATION OF SAMPLE SIZE

Approximately 184 participants are planned to be randomly assigned to either one of the following treatment groups: alternating use of SAR341402 and NovoLog or continuous use of NovoLog (in a 1:1 ratio), with a minimum of 146 evaluable participants (73 per treatment group) for the primary PK evaluation expected at the end of the study. If the number of study participants with evaluable PK data is determined to have been reached before all planned 184 participants are randomized, then the study randomization may be stopped sooner.

[figure not shown]
The sample size calculations were performed based on the expected variability of the primary PK endpoints AUClast, AUC, and Cmax following injection of a predefined, fixed dose of SAR341402 or NovoLog (ie, 0.15 U/kg) at Week 16.

A sample size of 146 evaluable participants (73 participants per arm) will ensure that the 90% CI for the estimated treatment ratio is within the acceptance range of [0.8 – 1.25] with at least 90% power; assuming a true ratio between 0.95 and 1.05 (switching arm / non-switching arm) and a total standard deviation on natural log scale of 0.35 or lower.

Sample size calculations were made using SAS® Software Version 9.4.

## 1.4 STUDY PLAN

The following figure describes the design of the study:

FPG: fasting plasma glucose; HbA1c: glycated hemoglobin A1c; PK: pharmacokinetics; T1DM: Type 1 diabetes mellitus; \* prior to the screening visit

The study comprises up to 4 periods:

- An up to 14-day screening period
- An up to 12-week run-in period (only for patients not treated with NovoLog and insulin glargine (100 U/mL) for at least 12 weeks before screening)
- A 16-week open-label treatment period:
  - Participants in the non-switching arm will receive NovoLog for 16 weeks,
  - Participants in the switching arm will receive NovoLog for the first 4 weeks, then SAR341402 for 4 weeks, followed by NovoLog for 4 weeks and then SAR341402 for the last 4 weeks.
- A 1-day post-treatment follow-up period.

The study duration per participant will be less than 19 weeks (for participants who do not require the run-in period) and less than 31 weeks (for participants who require the run-in period).

At the end of the 16-week open-label treatment period, patients will have blood sampling, including for PK determination, antibody measurements, HbA1c, and FPG. After blood sampling for the trough PK measurements, patients will receive a single SC injection of 0.15 U/kg SAR341402 (switching arm) or NovoLog (non-switching arm). Subsequently, PK sampling will be conducted for 8 hours according to assessment schedule; see pharmacokinetic flow chart in Section 1.3 of the protocol.

The end of treatment (EOT) is at Visit 7 (Week 16) after randomization. The end of the study (EOS) is a follow-up contact (Visit 8, recorded as Visit 8010 in the clinical database) at the time of Week 16 plus 1 day.

In case of premature permanent investigational medicinal product (IMP) discontinuation, the patients will have a premature treatment discontinuation visit (recorded as Visit 8000 in the clinical database), which will consist of all procedures planned for Visit 7 and is intended to be conducted before the definitive discontinuation of the IMP, or as soon as possible after discontinuation.

Patients who discontinue study intervention should remain in the study, with the remaining visits occurring as scheduled where possible, including the assessments planned in the SoA (see Section 1.3 of the protocol) except serial PK samples that should only be collected at the time of early discontinuation visit and do not need to be repeated at Visit 7 (Week 16).

- During the period of the COVID-19 (Coronavirus disease 2019) pandemic, protocol deviations may occur due to lockdown restrictions. On-site visits may not be performed according to the protocol schedule for some patients. In such cases, changes in study visit schedule are allowed as needed, to accommodate patient's safe access to study sites and study medication while minimizing risks to trial integrity and data collection: Intermediary on-site visits (Visits 5 and 6) may be replaced by over-the-phone or at-home visits, if feasible.
- The end of treatment visit (Visit 7), which is the most critical one for primary endpoint assessment, may be delayed so that the visit can be conducted on-site while preserving the patient's safety.

Consequently, the open-label treatment period and study duration may be extended by up to approximately 8 weeks, and the assessments collected at "Week 16" visit may be performed up to approximately 24 weeks after randomization. All delayed assessments will be included in the analyses. No risk is foreseen by continuing treatment with IMP beyond the planned 16 weeks in both treatment arms. These changes are temporary and will not be sustained once the pandemic is over. Any delayed assessments will be recorded in the protocol deviations.

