**Table 2 - Statistical analysis plan Statistical changes**

SAP Version Number	Date Approved	Rationale	Description of Statistical Changes
2.0	7-Jul-2020	Addition of COVID-19 related analyses	
Update of the disposition section to include the treatment/study discontinuations related to COVID-19.
 
Add a table of patient disposition by visit according to COVID-19 impact.
 
Add the definition of patients impacted by COVID-19, a table of the number of patients impacted or not by the COVID-19, along with the type of impact, and a listing of patients impacted.
 
Add a table of major or critical protocol deviations by COVID-19 impact.
 
Update the categories in the extent of IMP exposure table. Add an extent of IMP exposure table and IMP exposure tables by COVID-19 impact (Non-impacted, Impacted)
 
Add table of the number (%) of patients experiencing at least one treatment-emergent COVID-19 related adverse event by primary SOC and PT
 
Add immunogenicity, safety and efficacy subgroup

SAP Version Number	Date Approved	Rationale	Description of Statistical Changes
			analyses by COVID-19 impact (Non-impacted, Impacted).
2.0	7-Jul-2020	Addition of PK sensitivity analyses	Add PK sensitivity analyses

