### **2.1.3 Pharmacokinetic endpoints**

#### ***2.1.3.1 Primary pharmacokinetic endpoints***

The primary pharmacokinetic variables are the AUClast, AUC, and Cmax parameters following injection of a predefined, fixed dose of SAR341402 or NovoLog (0.15 U/kg) at Week 16. Further details for the derivation of PK parameters are given in [Section 2.5.7.1](#). Secondary pharmacokinetic endpoint.

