### ***Subgroup analyses***

If it will be deemed necessary for interpretation of results, PK parameters may also be summarized for selected subgroups.

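### Does keeping COVID-delayed Week 16 PK profiles in the primary analysis call for a required on-time-only analysis?

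*SAP*

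**What the plan says.** SAP 1.2.1 sets the objective as PK similarity "after 4x4-week periods of alternating administration of SAR341402 and NovoLog compared to 16-week continuous use of NovoLog". SAP 2.1.3.1 defines AUClast, AUC and Cmax "following injection of a predefined, fixed dose of SAR341402 or NovoLog (0.15 U/kg) at Week 16". In the switching arm the sequence ends with NovoLog for 4 weeks and "then SAR341402 for the last 4 weeks" (SAP 1.4). The protocol's schedules of activities (1.3.1 and 1.3.2) put Visit 7 at Day 112 with a window of 3 days either side.

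The COVID-19 text in SAP 1.4 relaxes this. Visit 7 may be postponed so that it can be held on site, so Week 16 assessments "may be performed up to approximately 24 weeks after randomization". Delays are logged as protocol deviations, and "All delayed assessments will be included in the analyses".

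SAP 1.6, Table 2, lists what version 2.0 added. One entry begins "Add immunogenicity, safety and efficacy subgroup" and concerns analyses by COVID-19 impact; PK is not in it. A separate entry reads "Add PK sensitivity analyses". In SAP 2.4.4.1 those sensitivity analyses are optional. One restores parameters excluded for major deviations, and the other removes implausible values or undocumented irregularities. On PK subgroups the SAP says: "If it will be deemed necessary for interpretation of results, PK parameters may also be summarized for selected subgroups".

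**The concern.** The primary endpoint seems to be treated less carefully than the tertiary ones. HbA1c and FPG get a planned split by COVID impact if numbers suffice, while PK gets none. If only the last period is stretched, a participant measured at Week 24 has had about 24 − 12 = 12 weeks of SAR341402 in that period instead of 4. The primary ANOVA has no term for timing, and neither optional sensitivity analysis isolates on-time profiles.

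At stake is whether the report shows equivalence for the regimen named in the objective, or for a mixture of that regimen and a longer one. If many profiles were late and PK changed with a longer final exposure, the pooled ratio would be a blend, and no required output would separate the parts.

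**Working it through.** **1. The plan's own figure.** Inputs from SAP 1.3: 73 evaluable per arm, log-scale SD 0.35, true ratio 0.95 to 1.05, 90% CI within 0.80 to 1.25. Exact power of the two one-sided tests (df = 2n − 3, integrated over the residual variance) is 0.903 at ratio 0.95, 0.910 at 1.05 and 0.971 at 1.00. The stated power of at least 90% is reproduced. Including or restricting delayed profiles changes nothing in this design calculation.

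**2. What an on-time-only analysis would look like.** The documents give no delay count. I assume 10, 20 or 30% delayed, equal in both arms, which leaves n = 66, 58 or 51 per arm. The CI factor is exp(t × 0.35 × √(2/n)).

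| Delayed (assumed) | n per arm | Power, ratio 0.95 | Power, ratio 1.00 | 90% CI factor |
|---|---|---|---|---|
| 0% | 73 | 0.903 | 0.971 | 1.101 |
| 10% | 66 | 0.875 | 0.954 | 1.106 |
| 20% | 58 | 0.832 | 0.923 | 1.114 |
| 30% | 51 | 0.782 | 0.880 | 1.122 |

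Power is below the planned level in every case, so the restricted set could only support the primary analysis and could not act as a second test.

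**3. What it could detect.** The restricted set is nested in the full set. If delay has no effect, the SE of the difference between the two log-ratios is 0.35 × √(2/n − 2/73), which gives 0.0189, 0.0295 and 0.0380. Chance alone then keeps the two ratios within exp(±1.96 × SE) of each other in 95% of trials: 0.964–1.038, 0.944–1.059 and 0.928–1.077.

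Now suppose, for illustration, a true ratio of 0.95 on time and 0.85 when delayed, with the NovoLog arm unaffected. Pooling a delayed share f moves the log-ratio by f × ln(0.85/0.95) = −0.111f.

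| f | Shift | Shift / SE | Chance of leaving the band |
|---|---|---|---|
| 0.10 | −0.0111 | 0.59 | 0.09 |
| 0.20 | −0.0222 | 0.75 | 0.12 |
| 0.30 | −0.0334 | 0.88 | 0.14 |

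In the other direction, at f = 0.20 the expected shift reaches the edge of the band only when |ln(delayed/on-time)| = 1.96 × 0.0295 / 0.20 = 0.289. With 0.95 on time, that is a delayed ratio of about 0.71 or 1.27. At f = 0.10 the lower figure is about 0.66. The comparison would look reassuring almost whatever the truth.

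**4. Does the Visit 7 window isolate the planned regimen?** Visit 6 is Day 84 ± 2 and Visit 7 is Day 112 ± 3. With both on time, the last period runs from 109 − 86 = 23 to 115 − 82 = 33 days. Under the COVID text, Visits 5 and 6, at which study drug is dispensed, may be held by phone or at home. A participant whose switch was displaced but whose Visit 7 was on time stays in the restricted set. One measured on Day 116 for a trivial reason leaves it.

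**5. Is there reason to expect an effect?** The endpoint follows one fixed dose, given after at least 8 hours without meal-time insulin (Protocol 4.1). Protocol 4.2 says there is no accumulation and no need for steady state. It also expects antibody responses about 2 weeks after first exposure and within 1 week after re-exposure, both inside a 4-week period. SAP 1.4 allows the extension in both arms.

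**6. Can the analyst follow the plan?** Yes. SAP 1.4 says that delayed assessments are analysed, and SAP 2.5.3 leaves nominal visits and PK visits as labelled. The examples of PK-excluding deviations in SAP 2.3.1 concern the injection on the profile day, not the visit date.

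**The case for a change.** The best case for a change is that the protocol's arguments are rationale and not data, and that the trial exists to find out whether switching alters exposure. A timing analysis chosen after results are known would be post hoc, and writing it in now costs a paragraph and one program rerun. Pooling could also mask a failure. If the on-time ratio were 0.80 and the delayed ratio 1.00, then with 10, 20 or 30% delayed the pooled ratio would be 0.818, 0.837 or 0.855, and the chance of passing would rise from 0.05 to 0.104, 0.190 or 0.310.

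The arithmetic stands, as does the point that no required output gives the in-window estimate. But the example needs a 25% rise in relative exposure from a longer final period, and nothing in the documents suggests one in either direction. A non-gating analysis would leave the pass decision unchanged. The possible post hoc choice is limited by SAP 1.4, which fixes the primary data set in advance, and by SAP 2.3.1, which requires every PK exclusion to be reported with its reason.

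Much of the descriptive information will also be there. SAP 2.2 tabulates COVID-affected visits, with a category for completed but delayed ones. Profiles from premature discontinuation are left out of the primary analysis (SAP 2.5.3), so the Visit 7 row shows how many primary PK visits were late. SAP 2.4.3.1 gives exposure beyond 16 weeks by arm. Neither table is confined to the PK population, which is a small gap in presentation. The optional PK subgroup summaries can be used if delays prove common.

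**Conclusion.** No change is needed. The missing text is real, but following the plan as written gives a well-defined primary analysis and no wrong result. Keeping delayed profiles is a fair trade: it protects the 73 evaluable per arm on which the 90% power rests, at the price of some variation in the length of the last period, on which single-dose PK is not expected to depend.

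The suggested addition would gain little. Under the assumptions of SD 0.35, 73 per arm before restriction, 10 to 30% delayed equally in both arms and an unaffected NovoLog arm, it would notice a delayed ratio of 0.85 against 0.95 about 9 to 14% of the time, and its own power at ratio 0.95 would be 0.875 to 0.782. Nor would it isolate the four 4-week periods. The power figures are for one parameter and are upper bounds on passing all three.

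This conclusion rests on the protocol's reasoning that delay does not matter, which the documents do not test, and on delay shares that they do not report. If late profiles turn out to be numerous, the report can describe delay and days since the last switch by arm and show the in-window estimate under the existing optional provisions.
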